12.5.2 PRIMARY EFFECTIVENESS ENDPOINTS

The primary effectiveness endpoints are

- the change from baseline in Tear Break-Up Time (TBUT), and
- the change from baseline in overall Meibomian gland score (MEIB)

Both endpoints will be evaluated at the 1 month visit.

Each of the primary endpoints will be analyzed using a linear mixed effects (LME) ANCOVA model. This will allow for the proper incorporation of within-person correlation into the statistical model, and will also allow for adjustment for baseline measurements. It should be noted that, as described in Section 12.2, the primary analysis on these two primary effectiveness endpoints will be based on the Cohort 2 per-protocol population.

Details of the LME models are provided in the Statistical Analysis Plan (SAP) provided in Appendix B. Hypotheses regarding the primary and secondary effectiveness outcomes are described below.

12.5.3 PRIMARY EFFECTIVENESS HYPOTHESES

The primary study hypotheses will demonstrate non-inferiority of the TearCare treatment as compared to LipiFlow, for both Tear Break-Up Time (TBUT) and overall Meibomian gland score (MEIB) in the Cohort 2 subjects (after SmartLid modification). The full statistical model for the analyses is described in the SAP (Appendix B).

To demonstrate non-inferiority of the TearCare treatment to the LipiFlow control for TBUT we will test the null hypothesis that $\beta_{1,TBUT}$ is less than the non-inferiority margin of 3 seconds:

$$H_0: \beta_{1,TBUT} \leq -3.0$$
$$H_A: \beta_{1,TBUT} > -3.0$$

Where $\beta_{1,TBUT}$ represents the difference in change from baseline (1 month – baseline, so positive is better) between the TearCare treatment and the LipiFlow control. The hypothesis will be tested by constructing a confidence interval (least squares mean interval) for $\beta_{1,TBUT}$ as described in the SAP.

To demonstrate non-inferiority of the TearCare treatment to the LipiFlow control for MEIB we will test the null hypothesis that $\beta_{1,MEIB}$ is less than the non-inferiority margin of 5 units:

$$H_0: \beta_{1,MEIB} \leq -5.0$$
$$H_A: \beta_{1,MEIB} > -5.0$$

Where $\beta_{1,MEIB}$ represents the difference in change from baseline (1 month – baseline, so positive is better) between the TearCare treatment and the LipiFlow control for the overall Meibomian gland score. The hypothesis will be tested by constructing a confidence interval (least squares mean interval) for $\beta_{1,MEIB}$ as described in the SAP.

Both hypotheses will be tested at a one-sided $\alpha = 0.05$. As both hypotheses will need to be rejected for study success there is no multiplicity adjustment necessary.

If non-inferiority of the TearCare device is established as described above, then we will proceed to test for superiority for each of the two primary endpoints, that is, we will repeat the two hypothesis tests with non-inferiority margins set to 0. If either of the two superiority tests is rejected then the TearCare device will be declared superior for that endpoint.

The primary effectiveness outcomes of the Cohort 1 per-protocol population will be summarized separately by descriptive statistics for continuous variables such as mean, median, standard deviation, minimum, and maximum.

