7 STUDY DESIGN

This is a prospective, randomized, controlled, single-masked, multi-center treatment study. This is a post-market study intended to collect data to update the indication for use for the TearCare System. To reduce potential bias in the study, study staff performing the endpoint assessments will be masked as to the subject's treatment arm. Subjects cannot be masked as it will be obvious to them which treatment they are receiving.

⁴⁰ Schiffman RM, Christianson MD, Jacobsen G, Hirsch JD, Reis BL. Reliability and validity of the Ocular Surface Disease Index. *Arch Ophthalmol* 2000;118: 615-621.

⁴¹ Schaumberg DA, Gulati A, Mathers WD, Clinch T, Lemp MA, Nelson JD, Foulks GN, Dana R. Development and Validation of a Short Global Dry Eye Symptom Index. *Ocular Surface*. 2007;5(1):50-57.

⁴² Amparo F, Schaumberg DA, Dana R. Comparison of Two Questionnaires for Dry Eye Symptom Assessment: The Ocular Surface Disease Index and the Symptom Assessment in Dry Eye. *Ophthalmology*. 2015;122(7):1498-1503.

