12.2 ANALYSIS POPULATIONS

The per-protocol analysis population includes all subjects who have at least one follow-up visit and have no major protocol deviations, including specifically no use of dry-eye medications (Xiidra, Restasis). The primary and secondary endpoint analysis will be performed based on the Cohort 2 per-protocol population.

The intent-to-treat (ITT) analysis population includes all subjects who are randomized to either arm, regardless of treatment received. As a sensitivity analysis, the primary and secondary endpoint analyses will also be carried out on the Cohort 2 ITT population as well.

The effectiveness outcomes for Cohort 1 subjects will be summarized descriptively based on the available data of the per-protocol population. The effectiveness data listings will be Cohort 1 subjects that are excluded from in the per-protocol population will be provided separately.

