- Using our estimates of β_1 and its standard error, carry out a t-test for the hypothesis.
- Form a confidence interval for β_1 and show that the lower bound is above -3.0 seconds,
- Calculate the least squares mean (LSM) at the mean baseline TBUT for the contrast between treatment and control, and its associated confidence interval, and show that the lower bound is above -3.0 seconds.

We will use the third (LSM) method since it provides the most flexibility, also allowing exploratory analyses examining the effects of other covariates, contrasts between groups, etc.

As is standard practice in non-inferiority studies, all tests will be carried out at a one-sided $\alpha = 0.05$ (or equivalently, using two-sided 90% confidence intervals).

The MEIB endpoint will use the same model and the same testing methods. To demonstrate non-inferiority of the TearCare treatment to the LipiFlow control for MEIB we will test the null hypothesis that β_1 is less than the non-inferiority margin of 5 units:

$$H_0: \beta_1 \leq -5.0$$

$$H_A: \beta_1 > -5.0$$

The study will be a success if the non-inferiority null hypothesis is rejected for both TBUT and MEIB. No alpha adjustments for multiplicity are necessary.

If the two non-inferiority nulls are rejected then each will be re-tested for superiority (that is, against 0.0 instead of the non-inferiority margin). If the TearCare device is superior to the LipiFlow control for either endpoint (or both) it will be declared superior for that endpoint (or both).

The linear mixed effects models can be fit in SAS or R as follows:

In SAS:

```
Proc Mixed data=TearCare method=ml;
  class SUBJ TRT;
  model TBUT_DIFF = TRT TBUT_BL / solution;
  random intercept / subject=SUBJ;
```

In R:

```
library(lme4)
fit.tbut <- lmer(TBUT.DIFF ~ TRT + TBUT.BL + (1|SUBJ) ,
  REML=FALSE, data=TearCare)
```

Note that since we are interested in testing the fixed effects, ML (maximum likelihood) versus REML (residual maximum likelihood) estimates are being used.

If the estimated between-subject variance $\hat{\sigma}_a^2$ is close to 0 we will repeat the analysis without the random intercept term (that is, as a standard ANCOVA without a random patient effect).

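### The superiority step allows a claim on either TBUT or MEIB at one-sided 0.05 each, with no multiplicity control: up to a 9.4% chance of at least one false claim if the devices are equal

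*Combined protocol and SAP*

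**What the plan says.** Protocol 12.5.3 tests non-inferiority on TBUT (margin 3 seconds) and MEIB (margin 5 units), each at one-sided 0.05, and gives this reason for leaving alpha alone: "As both hypotheses will need to be rejected for study success there is no multiplicity adjustment necessary". If both tests succeed, "we will repeat the two hypothesis tests with non-inferiority margins set to 0", and "If either of the two superiority tests is rejected then the TearCare device will be declared superior for that endpoint".

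SAP 22.1.1 has the same rule: if TearCare is "superior to the LipiFlow control for either endpoint (or both) it will be declared superior for that endpoint". On the level it says "As is standard practice in non-inferiority studies, all tests will be carried out at a one-sided" alpha of 0.05, equivalent to two-sided 90% intervals. Neither section orders the two superiority tests or divides alpha between them. The fixed sequence in 12.5.6 covers the seven secondary endpoints only.

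On the analysis set, 12.5.2 states that "the primary analysis on these two primary effectiveness endpoints will be based on the Cohort 2 per-protocol population". The superiority tests repeat the primary tests, so they use that set too. Section 12.2 adds: "As a sensitivity analysis, the primary and secondary endpoint analyses will also be carried out on the Cohort 2 ITT population as well".

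**The concern.** When success requires rejecting both nulls, testing each at 5% keeps the chance of a false success at 5% or less. The reason given in 12.5.3 is therefore sound for non-inferiority. The superiority step reverses the logic: one rejection out of two is enough for a claim. Two chances at 5% each do not hold the chance of any false claim at 5%.

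Moving from non-inferiority to superiority within one endpoint costs no alpha. The inflation comes only from having two endpoints, either of which can carry a claim. What is at stake is a pre-specified statement that TearCare is superior to a marketed competitor on a primary endpoint.

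A second, smaller matter is the population. Sections 9.9 and 12.2 remove subjects from the per-protocol set for treatment use after randomisation, and section 7 says of masking: "Subjects cannot be masked as it will be obvious to them which treatment they are receiving". Exclusions could therefore differ by arm. The documents do not allow the direction or size of any resulting bias to be worked out.

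**Working it through.** **Plan's own figures first (22.3).** At one-sided 0.05, 95% power and zero true difference, a two-sample t-test needs:

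- TBUT (SD 6.0 s, margin 3.0 s): 88 eyes per group, 176 in all. 176 × 1.4 = 246.4, taken as 246; 246/0.9 = 273.3, so 274 eyes, 137 subjects, 69 per group.
- MEIB (SD 9.0, margin 5.0): 71 eyes per group, 142 in all. 142 × 1.5 = 213; 213/0.9 = 236.7, so 237 eyes, 119 subjects.
- Joint power at correlation 0: 0.95² = 90.25%.

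All agree with the SAP.

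**Standard errors at the planned size.** 69 × 0.9 = 62.1 completers per arm, or 124.2 eyes.

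- SE(TBUT) = 6 × √(2 × 1.4/124.2) = 0.901 s
- SE(MEIB) = 9 × √(2 × 1.5/124.2) = 1.399 units

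**Non-inferiority gate when the devices are equal.** The probability of passing is Φ(margin/SE − 1.645).

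- TBUT: Φ(3.330 − 1.645) = 0.954
- MEIB: Φ(3.575 − 1.645) = 0.973
- Both, at correlation 0: 0.954 × 0.973 = about 0.93. The gate filters out very little.

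**Any false superiority claim, both true differences 0, correlation 0.** This is P(both pass the gate) minus P(both pass and neither superiority test rejects):

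0.9540 × 0.9732 − (0.9540 − 0.05) × (0.9732 − 0.05) = 0.0939, or 9.4%.

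Without the gate it would be 1 − 0.95² = 9.75%.

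**Other correlations and the alternatives**, from 4 million bivariate normal draws per setting with the gate applied and both differences 0:

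| Correlation | Current rule | Holm, overall 0.05 | TBUT then MEIB, 0.05 |
|---|---|---|---|
| 0 | 9.4% | 4.8% | 4.9% |
| 0.3 | 9.2% | 4.8% | 5.0% |
| 0.5 | 8.8% | 4.5% | 5.0% |
| 0.7 | 8.0% | 4.2% | 5.0% |
| 0.9 | 6.8% | 3.5% | 5.0% |
| 1 | 5.0% | 2.5% | 5.0% |

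Under the current rule each single-endpoint claim is false in 4.8% to 5.0% of trials.

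**Away from equality, current rule, correlation 0 to 0.5.** With TBUT equal and MEIB truly 1 unit worse, the rate is 5.3% to 5.6%. With TBUT 0.5 s worse and MEIB 1 unit worse, it is 2.0% to 2.2%. If TearCare is truly better on one endpoint, at most one superiority null is true, so the rate cannot exceed 5%.

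**The case against.** The strongest reply is that this step comes after success and is optional. The objective in section 2 is non-inferiority on both endpoints. A superiority claim is limited to the endpoint that earned it, and each such claim is held at 5% or less. Whether two endpoint-specific claims need joint control is partly convention, and the plan never promises it. The 9.4% is also the top of the range: it needs both differences at exactly zero and uncorrelated endpoints, and the documents give no correlation.

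Much of this stands as a limit on consequence. It does not rescue the reasoning: the justification offered does not apply to an either-endpoint rule. Equality on both endpoints is not a contrived case, because 22.3.1 and 22.3.2 size the trial on it. The plan also controls error across its secondary within-group tests in 12.5.6, while leaving its only formal tests of superiority over LipiFlow uncontrolled.

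On the population, both endpoints are graded by a masked assessor (9.8, 21.4, 21.8), and an ITT analysis is already planned. Masked grading limits measurement bias but does not prevent exclusions that differ by arm. The request changes which analysis leads; it does not add one. On imputation, 12.5.5 refers to the primary outcome without restricting it to TBUT, so the TBUT-only wording in 22.1.3 may be no more than a mismatch.

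Finally, the figures above use one data set for both the gate and superiority. They were not recomputed for a per-protocol gate followed by ITT superiority tests. The 5% bound still holds there, because Holm applied to valid ITT p-values controls the error whatever precedes it.

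**Conclusion.** The concern holds. If both true differences are zero, the plan gives a 5.0% to 9.4% chance of at least one false superiority claim over correlations from 1 down to 0, and 8.8% to 9.4% for correlations of 0.5 down to 0. That is close to twice the 5% set for each test unless the endpoints are highly correlated.

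The figures rest on the plan's SDs, inflation factors and 10% dropout, on normal approximations, and on an assumed range for the correlation. They are overall probabilities that include passing the gate. Among trials that have passed it, the rates are about 10.1% at correlation 0 and 9.4% at 0.5.

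The non-inferiority success rule, its power and the proposed indication are not affected. This should be corrected before the analysis, but it does not undermine the trial's main conclusion. The population point is a separate, unquantified weakness in the same step.

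**What to change.** In 12.5.3 and 22.1.1:

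1. State that after non-inferiority is shown on both endpoints, the two superiority hypotheses are tested with Holm at an overall one-sided level no higher than 0.05, or in a fixed order (TBUT, then MEIB only if TBUT rejects). Name the one chosen. An overall one-sided 0.025 with Holm is stricter (2.4%, 2.4% and 2.3% at correlation 0, 0.3 and 0.5) but is not needed to cure the multiplicity.
2. Base any superiority claim on the Cohort 2 ITT analysis, with the per-protocol result beside it, and extend the imputation in 22.1.3 to MEIB.

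These are wording changes. No subjects are added, and sample size and non-inferiority power stay as they are.

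The price is fewer superiority claims. The true effects below are illustrative assumptions, and the ranges are for correlation 0 to 0.5:

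| True TearCare advantage | Claim | Current | Holm 0.05 | TBUT first |
|---|---|---|---|---|
| TBUT 2 s and MEIB 3 units | At least one | 91% to 85% | 83% to 75% | 72% |
| MEIB 3 units only | MEIB | 66% to 68% | 55% to 57% | 3% to 5% |
| TBUT 2 s only | TBUT | 70% to 71% | 59% to 60% | 70% to 71% |

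The two procedures are not interchangeable. Holm keeps a claim on either endpoint within reach. TBUT-first order costs nothing on TBUT but nearly removes an MEIB-only claim, so it suits the sponsor only if TBUT is the superiority claim that matters.

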12.5.4 POOLABILITY

Using a linear mixed effects modeling approach described in Appendix B, poolability of the effectiveness outcomes for Cohort 2 per-protocol population will be evaluated across centers by testing a Treatment-by-Center interaction (TxC). If the TxC interaction is significant at $\alpha=0.15$ a Center effect will be included in the final model and results will be reported separately by Center. For this analysis, Centers with less than 5 enrolled subjects will be combined into a single virtual center.

12.5.5 MISSING DATA

As a sensitivity analysis, multiple imputations for the primary outcome at the 1 month time point will be carried out using baseline characteristics and 2-week outcomes as predictors. Details are provided in the SAP.

12.5.6 SECONDARY EFFECTIVENESS ENDPOINTS

The secondary effectiveness endpoints include change from baseline for the following outcomes:

1. Ocular Surface Disease Index (OSDI) score
2. Corneal staining scores
3. Conjunctival staining scores
4. Symptom Assessment iN Dry Eye (SANDE) scores
5. Eye Dryness Score
6. Number of Meibomian Glands Yielding any liquid
7. Number of Meibomian Glands Yielding clear liquid

If both primary effectiveness hypotheses are both met for the Cohort 2 per-protocol population, then we will sequentially test each of the secondary effectiveness endpoints based on the Cohort 2 per-protocol population to determine whether there is a significant change between baseline and 1 month. In each case we will test the null hypothesis that the change is 0 against the appropriate alternative (depending on the favorable direction). All testing of the secondary endpoints will be done using a two-sided alpha of 0.05. We will test the secondary endpoints in the order listed, stopping at the point where a test fails to reject. This sequential procedure controls the overall type I error rate for the secondary endpoints.

The secondary endpoints can be divided into two groups, those which are measured on a per-eye basis (Corneal Staining, Conjunctival Staining, Meibomian gland scores) and those measured on a per-subject basis (OSDI Score, SANDE Scores, Eye Dryness Score).

The per-eye secondary endpoints (Corneal Staining, Conjunctival Staining, Meibomian gland counts) will be tested using a similar linear mixed effects modeling approach as for the primary endpoint, with treatment as a fixed effect, and including a random intercept per subject to account for correlation.

The per-subject secondary endpoints (OSDI score, SANDE scores, Eye Dryness Score) are measured at the subject level so there is only one measurement per subject. For these endpoints a paired t-test will be used to evaluate change from baseline to 1 month.

The secondary effectiveness outcomes of the Cohort 1 per-protocol population will be summarized separately by descriptive statistics (mean, median, standard deviation,

minimum, and maximum for the continuous variables; count and percent for the categorical outcomes).

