2 STUDY OBJECTIVE

The objective of this study is to demonstrate the safety and effectiveness of a single TearCare® treatment compared to a single LipiFlow treatment to treat the signs and symptoms of dry eye disease in adult patients. This objective will be met by demonstrating non-inferiority of the TearCare treatment for each of the primary effectiveness endpoints.

This study is being conducted to collect data to support a modification to the TearCare indication for use to read as follows, “The TearCare® System is indicated for the treatment of the signs and symptoms of dry eye disease (DED).”

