4.2 PROPOSED INDICATION FOR USE

This study is being conducted to collect data to support a modification to the TearCare indication for use to read as follows:

“The TearCare® System is indicated for the treatment of the signs and symptoms of dry eye disease (DED).”

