6 STUDY ENDPOINTS

6.1 EFFECTIVENESS ENDPOINTS

This study will collect data to assess the impact of each treatment on the signs and symptoms of dry eye disease. Tear Break-Up Time and meibomian gland secretion scores, which measure the treatment effect of the device on the signs of dry eye disease, are the primary endpoints. The Ocular Surface Disease Index (OSDI) questionnaire, which is a validated instrument for measuring the severity of symptoms of dry eye disease, is the key secondary endpoint. The following other secondary endpoints have been chosen to collect additional data regarding changes in the signs and symptoms of dry eye disease in study subjects: Corneal and Conjunctival Staining, the Symptom Assessment iN Dry Eye (SANDE) questionnaire, the Eye Dryness Score, and Meibomian Gland Secretion Score (number of glands yielding clear liquid or any liquid at all).

For each outcome measure, results from the TearCare subjects will be compared with results from the LipiFlow subjects. All the primary and secondary endpoints will be at 1 month.

- **Primary effectiveness endpoints**
 - Mean Change from baseline in Tear Break-Up Time (TBUT)
 - Mean Change in the total Meibomian Gland Secretion Score³⁹

³⁹ Bron AJ, Benjamin L, Snibson GR. Meibomian gland disease. Classification and grading of lid changes. Eye 1991;5: 395–411.

- **Secondary effectiveness endpoints**
 - Mean Change from baseline in OSDI score⁴⁰
 - Mean Change from baseline in corneal staining scores
 - Mean Change from baseline in conjunctival staining scores
 - Mean Change from baseline in SANDE scores^{41,42}
 - Eye Dryness Score
 - Mean Change from baseline in the number of meibomian glands yielding clear liquid secretions
 - Mean Change from baseline in the number of meibomian glands secreting any liquid (clear or cloudy)
- **Additional Exploratory Endpoints**
 - Use of dry eye lubricants

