22 APPENDIX B – STATISTICAL ANALYSIS PLAN

22.1 EFFECTIVENESS ENDPOINTS AND ANALYSIS METHODS

22.1.1 PRIMARY EFFECTIVENESS ENDPOINT

The primary effectiveness endpoints are the change from baseline in Tear Break-Up Time (TBUT) and the total Meibomian gland secretion score (MEIB) at the 1 month follow up. Change is calculated as: 1 month – baseline, so a positive change is better. Both endpoints will be analyzed using a linear mixed effects (LME) model. This will allow for the proper incorporation of within-person correlation into the statistical tests, and will also allow for adjustment for baseline measurements. Both of these should increase the power over the simple “t-test using one eye” approach.

Since the SmartLid device was modified during the trial, all effectiveness analyses will be carried out with the Cohort 2 subjects only (i.e. subjects enrolled after the modified device was introduced). The primary effectiveness outcomes of the Cohort 1 subjects will be summarized separately by descriptive statistics (mean, median, standard deviation, minimum, and maximum).

The linear mixed effects model for TBUT can be written as follows:

$$y_{ij} = \beta_0 + \beta_1 T_i + \beta_2 TBUT_{ij,0} + b_{0i} + \epsilon_{ij}$$

Where

- $TBUT_{ij,k}$ is the TBUT value for subject i , eye j , week k .
- y_{ij} is the 1 month change from baseline TBUT for subject i , eye j .
$$y_{ij} = TBUT_{ij,4} - TBUT_{ij,0}$$
- T_i is the binary treatment indicator for subject i (0 = LipiFlow, 1 = TearCare)
- β_0, β_1 , and β_2 are the fixed effect parameters:
 - β_0 is the mean change from baseline for the LipiFlow arm,
 - β_1 is the difference between TearCare and LipiFlow in mean change from baseline,
 - β_2 is the effect of each unit change in baseline TBUT.
- b_{0i} is the random effect (random intercept term) for subject i
$$b_{0i} \sim N(0, \sigma_a^2)$$
- ϵ_{ij} is the normally-distributed error term
$$\epsilon_{ij} \sim N(0, \sigma_e^2)$$
- $\{b_{0i}\}$ and $\{\epsilon_{ij}\}$ are independent

To demonstrate non-inferiority of the TearCare treatment to the LipiFlow control for TBUT we will test the null hypothesis that β_1 is less than the non-inferiority margin of 3 seconds:

$$H_0: \beta_1 \leq -3.0$$

$$H_A: \beta_1 > -3.0$$

That is, we seek to reject the non-inferiority null hypothesis that the TearCare change in TBUT is more than 3 seconds worse than the LipiFlow change in TBUT.

For this model there are several equivalent ways to carry out this test:

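### OSDI, SANDE and Eye Dryness are tested only for change from baseline, on wording that pools the two arms, so the randomised control plays no part in the only planned inference on symptoms

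*Combined protocol and SAP*

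**What the plan says.** Section 6.1 says of OSDI, as the measure of the severity "of symptoms of dry eye disease, is the key secondary endpoint". It then states: "For each outcome measure, results from the TearCare subjects will be compared with results from the LipiFlow subjects".

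Section 12.5.6 sets out the secondary tests, done in a fixed order with OSDI first, at two-sided 0.05, in the Cohort 2 per-protocol population: "In each case we will test the null hypothesis that the change is 0 against the appropriate alternative". The per-eye secondaries use a mixed model "with treatment as a fixed effect, and including a random intercept per subject to account for correlation". For the three per-subject symptom scores the method is different: "For these endpoints a paired t-test will be used to evaluate change from baseline to 1 month".

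Section 12.2 defines the per-protocol population as all subjects with a follow-up visit and no major deviation, without reference to arm. Section 12.5.1 tabulates outcomes by visit and treatment group. SAP Section 22.1.4 adds no arm or contrast. It refers to 12.5.5 for the testing procedure, but that section is Missing Data; the procedure is in 12.5.6.

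**The concern.** A paired t-test of zero change has no treatment term. Applied to the population as defined, it pools TearCare and LipiFlow subjects, so a significant result could come from either arm. Applied within one arm, it is an uncontrolled before-and-after comparison. In neither case does the inference use the randomisation.

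This matters because both primaries are signs, while the trial is meant to support an indication covering signs and symptoms (Section 4.2). The three paired tests are the only planned inference on symptoms. Subjects are unmasked (Section 7) and rate themselves, and entry requires OSDI of 23 to 79 at the visit that also supplies the baseline. A before-and-after change therefore carries time effects and possible regression to the mean, which a randomised contrast would cancel.

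**Working it through.** **1. Subjects available.** The plan's own size reproduces: 88 eyes per group × 2 = 176; 176 × 1.4 = 246; 246/0.9 gives 274 eyes, or 137 subjects, rounded up to 69 per group (SAP 22.3.1). Then 69 × 0.9 ≈ 62 completers per arm, 124 pooled. The plan gives no power, SD of change or margin for OSDI.

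**2. SD of OSDI change (assumed).** Two routes from the pilots in Section 5.2:
- 2013, reading the p-values as paired t-tests: control 6.5/1.38 × √8 = 13.3; TearCare 17.4/3.25 × √10 = 16.9. The table does not name the test.
- 2017, SD = √(s₀² + s₁² − 2r·s₀·s₁) for pre/post correlation r from 0 to 0.7: TearCare (18.4, 12.2) 22.1 down to 13.2; control (19.9, 15.2) 25.0 down to 14.3.

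Working range: 13.3 to 25.

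**3. Pooled test, literal reading.** Let TearCare change by 0 and LipiFlow by 25.3 (41.0 − 15.7, the 2017 TearCare change, used as a scenario). The pooled mean is 12.65 and the pooled SD is √(SD² + 12.65²).

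| SD | Pooled SD | SE = pooled SD/√124 | Mean/SE |
|---|---|---|---|
| 13.3 | 18.4 | 1.65 | 7.7 |
| 25 | 28.0 | 2.52 | 5.0 |

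The critical value is 1.98, so the test is significant more than 99% of the time with no TearCare effect. With the smaller 2013 change (17.4) in LipiFlow and SD 25, mean/SE = 8.7/2.38 = 3.66, and the pass rate is still about 95% (Φ(3.66 − 1.98)).

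**4. Test in one arm.** Smallest significant observed fall = 2.00 × SD/√62: 3.4 points at SD 13.3 and 6.3 at SD 25. The 2017 warm-compress control itself fell 33.0 − 24.6 = 8.4 points. If TearCare repeats either pilot change (17.4 or 25.3), the test passes at least 99.9% of the time across the SD range, whatever LipiFlow does.

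**5. What a between-arm estimate would give.** With baseline in the model, residual SD = s₁√(1 − r²). From the 2017 SDs, r from 0 to 0.7, this is 12.2 to 8.7 (TearCare) and 15.2 to 10.9 (control). The 95% CI half-width is 1.98 × residual SD × √(2/62):
- residual SD 8.7: 3.1 points
- residual SD 15.2: 5.4 points

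A two-sided test would detect a true 5-point difference about 44% (residual SD 15.2) to 89% (8.7) of the time, and a 10-point difference at least 95% of the time. Per-protocol exclusions beyond the 10% dropout would lower these somewhat.

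**6. Per-eye secondaries.** Their model already has a treatment term. In the primary model of SAP 22.1.1 that coefficient "is the difference between TearCare and LipiFlow in mean change from baseline". The stated null of zero change is a different quantity, and the baseline term is not stated, but the contrast is available.

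**The case against.** The plan has reasonable defences. Section 6.1 promises a comparison, not a test or an interval, and the by-arm tables in Section 12.5.1 are a comparison of a kind. Section 2 ties the objective to the primaries alone: "This objective will be met by demonstrating non-inferiority of the TearCare treatment for each of the primary effectiveness endpoints". The proposed indication makes no claim against LipiFlow. The sponsor may simply have wanted to show improvement.

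Most of this stands as a limit on the point. The two sections are under-specified more than flatly contradictory. But the tables give no difference and no interval, and if improvement was the aim, the arm still has to be named.

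A reader might infer more than the documents support:
- That study success or the proposed indication fails. Success rests only on TBUT and gland secretion score.
- That the sponsor certainly intends to pool. That is the literal reading of Sections 12.2 and 12.5.6; intent is not stated.
- That the expected symptom change is mostly regression to the mean. Its size cannot be estimated from these documents.
- That a between-arm comparison would be too imprecise to be useful. Unadjusted change scores would give half-widths of 4.7 to 8.9 points at SD 13.3 to 25; the baseline-adjusted figures in step 5 are tighter.
- That a between-arm estimate would itself establish symptom benefit. The control is active, and the documents give neither a LipiFlow OSDI effect nor a margin.

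**Conclusion.** The point holds and should be fixed, although the primary conclusions do not depend on it. The textual finding needs no assumed figure: the key secondary and the two other symptom scores have no planned between-arm inference, and the stated population pools the arms. The size does rest on assumptions: 62 completers per arm and SDs taken from pilots of 18 and 24 subjects. On those, a significant paired result says almost nothing about TearCare relative to LipiFlow and, if pooled, need not reflect TearCare at all. The wrong section number in SAP 22.1.4 is clerical.

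**What to change.** Reconcile Sections 6.1, 12.5.6 and 22.1.4 before any outcome is analysed by arm.

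1. For OSDI, SANDE and Eye Dryness, pre-specify an ANCOVA of 1-month change on treatment and baseline, reported as the least-squares mean difference (TearCare minus LipiFlow) with a 95% CI. Make no non-inferiority claim on symptoms unless a justified margin is fixed before unmasked analysis.
2. If the paired tests are kept, run them within a named arm (TearCare, or each arm separately), not pooled, and label them as within-arm change.
3. For the per-eye secondaries, report the treatment coefficient of the planned mixed model, with baseline as covariate, as the between-arm estimate.
4. Correct the reference in 22.1.4 from 12.5.5 to 12.5.6.

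The cost is wording and a little more analysis; all three scores are already collected at baseline and 1 month in both arms. The contrast will not remove expectation effects that differ between unmasked arms, and it may not settle differences of about 5 points or less.
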